Protocol
Study ID: GH-4831
U1111-1264-1805
EU PAS No.: Study not yet registered

~~CONFIDENTIAL~~

Date:
Version:
Status:
Page:

21 February 2022
10.0
Final
1 of 58

Novo Nordisk

Protocol

Study ID:

CROITRE Registry :French registry of children treated with Norditropin[®] for short stature associated with Noonan Syndrome (PASS)

*Redacted protocol
Includes redaction of personal identifiable information only.*

~~This confidential document is the property of Novo Nordisk. No unpublished information contained herein may be disclosed without prior written approval from Novo Nordisk. Access to this document must be restricted to relevant parties.~~

Study information

Title	French registry of children treated with Norditropin [®] for short stature due to Noonan Syndrome (PASS)
Protocol authors	[REDACTED], Novo Nordisk France [REDACTED]
Protocol version identifier	9.0
Date of last version of protocol	15 February 2022
EU PAS Register number	Study not yet registered
Active substance	Somatropin (ATC code :H01AC01)
Medicinal product	Norditropin [®]
Product reference	
Procedure number	GH-4831
Marketing authorisation holder(s)	Novo Nordisk
Joint Post Authorisation Safety Study (PASS)	Yes
Research question and objectives	
The present study has been designed to develop a French registry of children treated with Norditropin[®] for short stature due to Noonan Syndrome (NS).
 
The primary objective is to describe the long-term change of height in children treated with Norditropin[®] for short stature due to NS over a 4-year period* in routine clinical practice in France.
 
The secondary objectives apply to children treated with Norditropin[®] for short stature due to NS:
 
• To describe the long-term safety profile of Norditropin[®] in children with short stature due to NS• To describe the socio-demographic and clinical characteristics of NS children treated with Norditropin[®]• To describe the therapeutic care of NS children treated with Norditropin[®]

* The follow-up period in this study is 4 years with possibility of extension for patients who did not reach adult height.

Table 11 Precision of the primary criteria depending on the number of evaluable patients.....	37

List of abbreviations

ADHD	Attention deficit hyperactivity disorder
AE	Adverse Event
ADR	Adverse Drug Reaction
AMH	Anti-Müllerian Hormone
BMI	Body Mass Index
CBC	Complete Blood Count
CI	Confidence Interval
CNIL	French Data Protection Agency
CPP	Committee for Protection of Persons
CRF	Case Report Form
CRO	Contract Research Organisation
CT	Transparency Committee
CTCAE	Common Terminology Criteria for Adverse Events
CV	Coefficient of variation
GAS	Growth Analysis Set
ECG	Electrocardiogram
EDC	Electronic Data Capture
eCRF	Electronic Case Report Form
EU PAS	The EU electronic register of post-authorisation studies maintained by the European Medicines Agency
FAS	Full Analysis Set
FSH	Follicle-Stimulating Hormone
FT4	Free Thyroxine
(rh)GH	(recombinant human) Growth Hormone
GHD	Growth Hormone Deficiency
GPP	Good Pharmacoepidemiology Practice
GVP	Good Pharmacovigilance Practice
HAS	French National Authority for Health
Hb	Haemoglobin
HbA_{1c}	Haemoglobin A_{1c}
HDL	High-density lipoproteins

(HR)QoL	(Health Related) Quality of Life
Ht	Haematocrit
IEC	Independent Ethics Committee
IRB	Institutional Review Board
IGF-1	Insulin-like growth factor 1
IGFBP-3	IGF Binding Protein-3
ISPE	International Society for Pharmacoepidemiology
LAR	Legally Acceptable Representative
LDL	Low-density lipoproteins
LH	Luteinizing Hormone
LVES	Left Ventricular Ejection Fraction
LVFS	Left Ventricular Fractional Shortening
MAH	Marketing Authorisation Holder
MedDRA	Medical Dictionary for Regulatory Activities
MCH	Mean Corpuscular Haemoglobin-
NAH	Near Adult Height
NIS	Non-interventional Study
NS	Noonan Syndrome
PASS	Post Authorisation Safety Study
PMP	Project Management Plan
PT	Prothrombin Time
PTT	Partial Thromboplastin Time
SAE	Serious Adverse Event
SADR	Serious Adverse Drug Reaction
SAS	Safety Analysis Set
SDS	Standard Deviation score
SMR	Service Medical Rendu
TSH	Thyroid-Stimulating Hormone
ULIS	Units localized for school inclusion

2 Responsible parties

In this document physician refers to the individual overall responsible for the conduct of the Non-Interventional Study (NIS) at a study site.

3 Abstract

- **Title:** French registry of children treated with Norditropin[®] for short stature due to Noonan Syndrome-NS (PASS)

Planned milestones:

Milestone	Planned date
Start of data collection (FPFV)	March 2022
Last Patient First Visit (LPFV)	March 2024
Last Patient Last Visit (LPLV)	March 2028
Study progress reports	Monthly update during implementation, inclusion & follow-up
Interim report of study results	October 2025
Final report	August 2028

Background and Rationale:

Norditropin[®] (NN-220; somatropin; Novo Nordisk A/S, Denmark), a recombinant human growth therapy (rhGH) produced by genetic recombinant technology, is currently the sole approved medication for the treatment of short stature due to NS in France. In October 2020, the Transparency Committee (CT- *Commission de Transparence*) rated the actual clinical benefit (SMR- *Service Medical Rendu*) of Norditropin[®] as “important” and issued a favourable opinion for inclusion of Norditropin[®] on the list of reimbursed proprietary medicinal products in NS children with short stature (< -2 SDS)(1).

Despite the existing literature documenting the effect of GH therapy on height outcomes, long-term effectiveness and safety data associated with Norditropin[®] treatment is needed. Furthermore, information on quality of life in NS patients remains scarce. Hence, the CT has requested the development of a national registry of NS children with short stature and treated with Norditropin[®] until adulthood. Data should be available within five years. This registry shall provide information on long-term clinical evolution of these patients (e.g adult height and quality of life) and on the safety profile of Norditropin[®] (notably the risk of tumour, effect on glucose metabolism and cardiac defects). The CT has also recommended that data collection be defined in collaboration with French reference and competence centres.

To respond to the CT request, Novo Nordisk will establish a French registry of NS children treated with Norditropin[®] for short stature to assess the long-term growth evolution and safety of

Norditropin[®]. Children will be followed-up for 4 years (with possibility of extension for patients who did not reach adult height) in hospital setting notably in French reference/competence centres specialized in the care of short stature due to NS (the rare endocrine disorders network referred as FIREENDO). This registry also aims to collect data on quality of life, clinical, genetic, and other relevant NS characteristics.

Objectives:

The primary objective is to describe the long-term change of height in children treated with Norditropin[®] for short stature due to NS over a 4-year period* in routine clinical practice in France.

All secondary objectives (as follows) apply to children treated with Norditropin[®] for short stature due to NS:

- To describe the long-term safety profile of Norditropin[®]
- To describe the socio-demographic and clinical characteristics of patients
- To describe the therapeutic care of patients:
 - Describe GH treatment patterns
 - Describe other NS treatments
- To describe the NS in terms of auxological characteristics, diagnosis, and NS comorbidities
- To describe the change in health-related quality of life (HRQoL) of patients and their parents /Legally Acceptable Representative (LAR)

The exploratory objectives are as follows:

- To identify driving factors that are associated with HRQoL
- To identify driving factors that are associated with change in height (SDS) over a 4-year period[†]

Description of type of study and treatment of patients

This study is a PASS. This is a non-interventional registry of children treated with Norditropin[®] for short stature due to NS. This study presents both a prospective and retrospective design. Data will be collected for 3 groups of patients:

[figure not shown]
- Incident patients: Children initiating Norditropin[®] upon their inclusion in the study
- Prevalent patients: Children who were already treated with Norditropin[®] before their inclusion in the study and finished their growth upon their inclusion. For these patients, all data will be collected retrospectively from medical records

* The follow-up period in this study is 4 years with possibility of extension for patients who did not reach adult height.

- **Prevalent patients:** Children who were already treated with Norditropin® before their inclusion in the study and who did not finish their growth upon their inclusion. For these patients, data will be collected both retrospectively and prospectively

HRQoL data will be collected on incident patients only. The inclusion period will last for 24 months and patients will be followed-up for 4 years, with possibility of extension for patients who did not reach adult height. This will allow to provide interim results on October 2025 to the French National Authority for Health (HAS). A total of 9 visits (1 inclusion visit: D0 and 8 follow-up visits: M6, M12, M18, M24, M30, M36, M42, M48) are planned. Each visit is allowed within one-month window. All information will be collected as per physicians' routine of care.

The design of the registry is displayed below :

Eligibility criteria .

Inclusion criteria

- Patients with a clinical and/or genetic diagnosis of NS
- Patients who are treated with Norditropin® (already treated or initiating) and who are followed in a participating centre
- The decision to initiate treatment with commercially available Norditropin® has been made by the patient/parents/Legally Acceptable Representative (LAR) and the treating physician before and independently from the decision to include the patient in this study.

Exclusion criteria

For an eligible patient, all exclusion criteria must be answered “no”.

- Patients/Parents/LAR opposed to the collection and processing of their children’s medical data.
- Mental incapacity, unwillingness or language barriers precluding adequate understanding or cooperation

Withdrawal criteria

- Patient withdrawal (opposition)
- Lost to follow-up
- Death

Key assessment variables

Norditropin[®] treatment patterns

- Date at start (baseline)
- Dose at Norditropin[®] treatment start in mg/kg/day (baseline)
- Date at the end of treatment (at one of the follow-up visit)
- Dose of Norditropin[®] in mg/kg/day at the end of follow-up (at one of the follow-up visit)

Auxological characteristics

- Age at gestational age in weeks (baseline)
- Weight at birth, 1 year, 2 years and 3 years of age in kg (baseline)
- Length at birth, 1 year, 2 years and 3 years of age in cm (baseline)
- Head circumference at birth, 1 year, 2 years and 3 years of age in cm (baseline)
- Mother’s height in cm (baseline)
- Father’s height in cm (baseline)
- Adult height (AH) in SDS (at one of the follow-up visit)

Health-Related Quality of Life

- PedsQL score (from baseline until end of follow-up)

Data sources

The data required to address the registry objectives come from the medical records, prescription records, laboratory and questionnaires administered to patients (patient reported outcomes-PROs). Study investigators (or clinical research associates (CRAs) will capture data through an e CRF.

HRQoL will be collected directly from incident patients and their parents by using a self-administered validated quality of life questionnaire (PedsQL).

- **Number of patients to be studied**

According to experts' input, a maximum of 50 eligible incident patients could be included during the 24 months inclusion period. It is expected that the number of eligible patients initiating Norditropin[®] before 2020 would be lower since that there was no market authorisation for this indication yet and would not exceed 30 patients per year. Considering that eligible prevalent patients initiated Norditropin[®] from 2010, that 79% of solicited sites will be participating in the study (30 sites over 38) and that 80% of eligible patients will be included (excluding opposition, patient not regularly followed by this site), it is estimated that a maximum of 221 patients will be included in the registry.

Finally, the proportion of evaluable patients for the primary criteria (patients that have height measurements until the end of their 4 years follow-up or until they reach adult height (AH)) is planned to be 80%. Therefore, it is estimated that this study will enrol a maximum of 177 patients evaluable for the primary criteria.

Data analysis

There are 3 patients population considered in this study:

- Overall population: All patients included in the eCRF.
- Full Analysis Set (FAS): All patients included in the eCRF and meeting all selection criteria. All secondary analyses will be performed on FAS.
- Growth Analysis Set (GAS): All patients from the FAS for which the primary criteria can be evaluated, i.e. height measurements available until the end of the 4-year follow-up or AH is reached, whatever occurs first.

A descriptive analysis will be conducted on all study endpoints for which data has been collected both on FAS (GAS for primary endpoint) and per subgroups of interest as long as that the sizes of the subgroups are relevant for statistical estimations.

4 Amendments and updates

None.

5 Milestones

Table 1 Milestones

Milestone	Planned date
Start of data collection (FPFV)	March 2022
Last Patient First Visit (LPFV)	March 2024
Last Patient Last Visit (LPLV)	March 2028
Study progress reports	Monthly update during implementation, inclusion & follow-up

Protocol
Study ID: GH-4831
U1111-1264-1805
EU PAS No.: Study not yet registered

~~CONFIDENTIAL~~

Date: 21 February 2022
Version: 10.0
Status: Final
Page: 14 of 58

Novo Nordisk

Milestone	Planned date
Interim report of study results	October 2025
Final report	August 2028

6 Rationale and background

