8.1 Study design

This study is a PASS. This is a non-interventional registry of children treated with Norditropin® for short stature due to NS. This study aims to provide data on long-term growth evolution and safety of Norditropin® as well as HRQoL data. This registry will include the entirety of children treated with Norditropin® for short stature due to NS over the inclusion period. In consequence, this registry will enroll both patients who received Norditropin® before its marketing authorization for short stature due to NS in France and patients who received Norditropin® after its approval.

This study presents both a prospective and retrospective design. Data will be collected for 3 groups of patients:

- Incident patients: Children initiating Norditropin® upon their inclusion in the study.
- Prevalent patients:
 - Children who were already treated with Norditropin® before their inclusion in the study and finished their growth upon their inclusion. For these patients, all data will be collected retrospectively from medical records.
 - Children who were already treated with Norditropin® before their inclusion in the study and who did not finish their growth upon their inclusion. For these patients, data will be collected both retrospectively and prospectively.

HRQoL data will be collected on incident patients only.

The inclusion period will last for 24 months and patients will be followed-up for 4 years with possibility of extension for patients who did not reach AH. This will allow to provide interim results on October 2025 to the HAS.

All information will be collected as per physicians' routine of care and as this study is non-interventional, neither clinical interventions nor laboratory assessments will be imposed as per this protocol.

* The follow-up period in this study is 4 years with possibility of extension for patients who did not reach adult height.

[figure not shown]

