8.1.1.2 Secondary endpoints

Secondary objective-1: To evaluate the long-term safety profile of Norditropin®.

All drug related adverse reactions (ADR), serious adverse drug reactions (SADR), serious adverse events (SAE) and adverse events (AE) will be recorded and described up to the end of growth development or end of follow-up if earlier. The endpoints related to the secondary objective-1 are listed in [Table 3](#).

Table 3 Secondary endpoints in relation to secondary objective 1

Title of endpoint	Time frame	Unit
Number of adverse drug reactions (ADR)	From start of Norditropin® until end of follow-up	Count of events
Number of serious adverse drug reactions (SADR),	From start of Norditropin® until end of follow-up	Count of events
Number of serious adverse events (SAE)	From start of Norditropin® until end of follow-up	Count of events
Number of adverse events (AE)	From start of Norditropin® until end of follow-up	Count of events

Secondary objective-2: To describe the socio-demographic and clinical characteristics of patients. The endpoints related to the secondary objective-2 are listed in [Table 4](#).

Table 4 Secondary endpoints in relation to secondary objective 2

Title of endpoint	Time frame	Unit
Socio-demographic		
Education	From start of Norditropin® treatment until end of follow-up	NA
School level	From start of Norditropin® treatment until end of follow-up	NA
Educational measures	From start of Norditropin® treatment until end of follow-up	NA
Clinical characteristics		

Title of endpoint	Time frame	Unit
Tanner stage	At all visits	NA
Change in pulse rate	From start of Norditropin® treatment until end of follow-up	Beats per minute
Change in diastolic blood pressure	From start of Norditropin® treatment until end of follow-up	mm Hg
Change in systolic blood pressure	From start of Norditropin® treatment until end of follow-up	mm Hg
Change in corrected QT-interval (Electrocardiogram)	From start of Norditropin® treatment until end of follow-up	msec
Change in echocardiogram parameters	From start of Norditropin® treatment until end of follow-up	mm (Left ventricular interventricular septal maximum thickness in diastole) mm (Left ventricular end diastolic diameter) % (Left Ventricular Fractional Shortening (LVFS)) % (Left Ventricular Ejection Fraction (LVEF)) Cm/s (Diastolic function (Ea)) Cm/s (Diastolic function (Aa))

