8.2.8 Visit procedures

8.2.8.1 Study flow chart

Table 9 Study flow-chart

	Baseline (M0)	M6	M12	M18	M24	M30	M36	M42	M48
Inclusion/Exclusion criteria	X								
Socio-demographic characteristics									
Year of birth	X								
Sex	X								
Education, school level and educational measures	X	X	X	X	X	X	X	X	X
Clinical characteristics									
Age of onset of puberty	X								
Date of onset of menstruations (female only)	X								
Tanner stage	X	X	X	X	X	X	X	X	X
Comorbidities of interest not related to NS	X								
Pulse rate	X	X	X	X	X	X	X	X	X
Blood pressure (diastolic, systolic)	X	X	X	X	X	X	X	X	X
Echocardiogram parameters	X		X		X		X		X
Corrected QT interval (QTc) (measured by electrocardiogram (ECG))	X		X		X		X		X
Complete blood count (CBC)	X	X	X	X	X	X	X	X	X
Haemostasis parameters	X								
IGF-1 level	X	X	X	X	X	X	X	X	X
IGFBP-3 level	X								
TSH level	X								
FT4 level	X								
HbA _{1c} level	X		X		X		X		X
Fasting insulin blood level	X		X		X		X		X
Fasting glucose blood level	X		X		X		X		X
Fasting total cholesterol	X		X		X		X		X

	Baseline (M0)	M6	M12	M18	M24	M30	M36	M42	M48
Fasting triglycerides	X		X		X		X		X
Fasting HDL level	X		X		X		X		X
Fasting LDL level	X		X		X		X		X
Fasting Ratio total cholesterol/ HDL level	X		X		X		X		X
Parameters of gonadal function (inhibin B, AMH, LH, FSH, oestradiol / testosterone)	X		X		X		X		X
NS characteristics									
Auxological characteristics									
Gestational age at birth	X								
Head circumference at birth, at 1 year, at 2 years and 3 years of age	X								
Weight at birth, at 1 year, at 2 years and 3 years of age	X								
Length at birth, at 1 year, 2 years and 3 years of age	X								
Height velocity in the first year/ 6 months preceding Norditropin® start	X								
Weight at Norditropin® start	X	X	X	X	X	X	X	X	X
Height at Norditropin® start	X	X	X	X	X	X	X	X	X
Father 's height	X								
Mother's height	X								
Adult height (NAH)	X								
Bone age	X		X		X		X		X
Diagnosis									
Familial form of Noonan	X								
Parent affected	X								
Age of clinical diagnosis of NS	X								
Date of molecular diagnosis	X								
Molecular diagnosis (Type of NS-related genes mutated, and variant identified)	X								
NS comorbidities									

	Baseline (M0)	M6	M12	M18	M24	M30	M36	M42	M48
NS comorbidities	X	X	X	X	X	X	X	X	X
Therapeutic care									
Norditropin® treatment patterns									
Date of start	X								
Dose at start	X								
Dose titration		X	X	X	X	X	X	X	X
Dose at the end of treatment		X							

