8.7 Data analysis

8.7.1 Definition of analysis sets

The site populations will be defined as follows:

- Contacted sites: all reference and competence centres in France will be solicited to participate in this study
- Participating sites: all sites that agreed to participate in the study
- Active sites: all sites that included at least one eligible patient

The sites main characteristics (localisation, size) will be compared to ensure that the active sites are representative at the national level.

There are 3 patients population considered in this study:

- Overall population: all patients included in the eCRF,
- Full Analysis Set (FAS): all patients included in the eCRF and meeting all selection criteria. All secondary analyses will be performed on FAS.

- Growth Analysis Set (GAS): all patients from the FAS for which the primary criteria can be evaluated, i.e. height measurements available until the end of the 5-year follow-up or until NAH is reached, whatever occurs first.

The subgroups of interest for analyses are defined as follows:

- Norditropin[®] treatment duration: depending on age of onset and age at puberty onset, the patients may have shorter or longer time under GH treatment, which may highly influence auxological outcomes
- Mutated gene: PTPN11, SOC2, other

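### The Growth Analysis Set is defined by adult height and 4 years in the abstract but by near adult height and 5 years in section 8.7.1, so membership of the primary analysis population depends on the section applied

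*Protocol*

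**What the plan says.** The Growth Analysis Set is defined twice.

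- Protocol abstract, data analysis: heights must be available to the end of a 4-year follow-up or until "AH is reached, whatever occurs first". The abstract spells AH out as adult height where it discusses patient numbers. Section 8.5 uses the same rule, 4 years or adult height, and attaches the planned 80% evaluable share to it.
- Protocol section 8.7.1: "height measurements available until the end of the 5-year follow-up or until NAH is reached, whatever occurs first". The list of abbreviations gives NAH as near adult height.

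The collected item also has two names. Table 9 labels its row "Adult height (NAH" (closing bracket omitted here), joining the two terms. The abstract lists it as "Adult height (AH) in SDS (at one of the follow-up visit", and section 8.2.10 and Table 10 also call it AH.

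The height that ends the primary change is set elsewhere. Table 2 runs from the start of treatment to the end of follow-up and names no growth milestone. Section 8.7.2.1 stops at the end of follow-up or at GH, whichever comes first. The abbreviation list gives GH as growth hormone.

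**The concern.** The protocol gives the two terms different meanings, and by its name near adult height is reached no later than adult height. The two definitions differ in both the milestone and the follow-up length, so they cannot both be applied.

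Two things are at stake. The first is who enters the only population used for the primary endpoint. The second is the adult-height result. The abstract and section 6.2 report that the Transparency Committee named adult height among the outcomes the registry should provide. A field labelled as adult height but abbreviated as near adult height leaves room for near adult values to be reported under that name.

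**Working it through.** **The plan's own figures.** Section 8.5 gives at most 30 starts per year from 2010 (10 years to 2020), 50 incident patients, 30 of 38 sites, 80% of eligible patients included, 80% evaluable, a coefficient of variation of 20% and a two-sided 95% interval.

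- Included: (30 × 10 + 50) × 30/38 × 0.80 = 221.05. Stated: 221.
- Evaluable: 221 × 0.80 = 176.8. Stated: 177.
- Relative half-width: 1.96 × 0.20 / √177 = 2.946%. Stated: 2.95%.

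All three reproduce. The 80% belongs to the rule of 4 years or adult height. No share is given for the rule in 8.7.1.

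**The passages side by side.**

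| Place | Growth milestone | Follow-up |
|---|---|---|
| Abstract, Growth Analysis Set | AH | 4 years |
| 8.5, evaluable patients | adult height | 4 years |
| 8.7.1, Growth Analysis Set | NAH | 5 years |
| 8.7.2.1, primary change | GH | end of follow-up, no length |
| Table 2, primary endpoint | none | end of follow-up, no length |
| Table 9, collected item | adult height, abbreviated NAH | – |
| Abstract list, 8.2.10, Table 10 | AH | – |

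**Applying the two set definitions to individual children.** A child is evaluable if heights are available up to the earlier of the milestone and the end of follow-up.

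1. Heights stop after NAH, before AH and before 4 years: in the set under 8.7.1, out under the abstract.
2. Heights run to 4 years and stop there, with NAH not yet reached: in under the abstract, out under 8.7.1.
3. Heights run past both milestones within 4 years: in under both.

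Cases 1 and 2 show that neither set contains the other. The NAH wording admits more children and the 5-year wording admits fewer. Case 2 can arise on the planned schedule: visits end at M48, and the last first visit (March 2024) is 4 years before the last visit (March 2028).

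**Effect on precision.** The evaluable share under 8.7.1 is unknown, so I vary it as an assumption.

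- 70%: 221 × 0.70 = 154.7, about 155 children; 1.96 × 0.20 / √154.7 = 3.15%.
- 90%: 221 × 0.90 = 198.9, about 199 children; 1.96 × 0.20 / √198.9 = 2.78%.

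The number of children matters little to the planned precision. What changes is which children are described.

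**What cannot be computed.** Section 8.7.2.1 defines SDS as height minus the reference mean, divided by the reference SD, on the French growth curve. For a child of height h1 at NAH and h2 at AH, the difference is (h2 − m2)/s2 − (h1 − m1)/s1, where m and s are the reference mean and SD at each point. The protocol gives none of these six values. It also gives no count of children reaching either milestone.

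**The case against.** **Loose wording.** The strongest reply is that the two terms are used as synonyms. NAH appears only in the abbreviation list, Table 9 and 8.7.1, while the other evaluability statements and the extension rule say adult height. That is plausible, but the protocol never says so and its abbreviation list points the other way. Section 8.7.1 is also the formal definition of the analysis sets, so an analyst would reasonably start there.

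**Left to the SAP.** An operational rule for adult height may properly sit in the SAP or the case report form, and its absence here is not criticised. The contradiction is different: the protocol states two rules, and a SAP following one departs from the other. The only detail that 8.7.2 expressly defers to the SAP concerns the exploratory models.

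**Stronger readings that the document does not support.**

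- A reader might infer that the AH/NAH mismatch itself changes the end height. It is not shown. The two set definitions decide evaluability; Table 2 and 8.7.2.1 set the end value, and they name neither AH nor NAH.
- A reader might assume some residual growth in centimetres, divide by an adult height SD, and compare the result with the claimed half-width of 2.95% × 1.14 = 0.034 SDS. That treats the reference mean as flat between the two points. If it rises, the SDS shift may be near zero or negative. The residual growth, the SD and the share of children would all be assumed.
- A reader might infer that the prevalent cohort split ("finished their growth upon their inclusion") or the adverse-event window ("up to the end of growth development or end of follow-up if earlier") changes too. Neither phrase names AH or NAH. The extension rule says adult height throughout, so there is no conflict there.
- Table 9 might be read as a second NAH rule. It is a collection schedule and closes nothing; it is evidence that the terms are conflated.

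**Conclusion.** The concern holds as an inconsistency in the definition of the primary analysis population. The abstract and 8.5 give one rule and 8.7.1 gives another. They differ in milestone and in follow-up length, and they classify some children differently. Section 8.7.2.1 adds a third wording for the end of the primary change, and Table 9 leaves unclear whether the recorded value is an adult or a near adult height.

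The conclusion about the milestone rests on one premise: near adult height, by its name, comes no later than adult height. The conflict over follow-up length needs no such premise. How many children are affected is unknown, and no size or direction can be given for the mean SDS change. The planned precision is barely touched. This is worth correcting before the analysis set is fixed because it concerns the primary population and is cheap to settle. It is not evidence that the primary result would be biased in a known direction.

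**What to change.** Use one milestone, adult height, and one follow-up length in the abstract, 8.5, 8.7.1, 8.7.2.1, Table 9 and Table 10. Adult height matches the authority's request and most of the protocol. Replace GH in 8.7.2.1 in the same edit, so that the end of the primary change and the analysis-set rule name the same event.

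Apply one definition of adult height to all children. It can be written in the protocol or the SAP, with its content settled by the scientific committee. It must allow for children who cannot be classified: section 8.2.8.2 expects missing data, section 8.4 does not require unavailable data, and some prevalent children are wholly retrospective. Flag heights known only to be near adult so that they are not reported as adult height.

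The cost is protocol and table wording plus one flag. Children whose heights stop between the two milestones, before the end of follow-up, leave the main description and appear in a sensitivity description. I would expect them to be few, but the protocol gives no count. No new assessment is needed.
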